#### 3.2 Exclusion Criteria

3.2.1 Participants who are receiving any other investigational agents.

3.2.2 Participants with purely non-secretory MM [absence of a monoclonal protein (M protein) in serum as measured by electrophoresis and immunofixation and the absence of Bence-Jones protein in the urine defined by use of conventional electrophoresis and immunofixation techniques and the absence of involved serum free light chain >100 mg/L]. Patients with light chain MM detected in the serum by free light chain assay are eligible.

3.2.3 Participants with Plasma Cell Leukemia

3.2.4 Because of compromised cellular immunity, patients who have a known human immunodeficiency virus (HIV), active hepatitis C virus (HCV) or active hepatitis B virus (HBV).

3.2.5 Myocardial infarction within 6 months prior to enrollment or New York Heart Association (NYHA) Class III or IV heart failure (see Appendix H), uncontrolled angina, severe uncontrolled ventricular arrhythmias, or electrocardiographic evidence of acute ischemia or active conduction system abnormalities. Prior to study entry, any ECG abnormality at screening will be documented by the investigator as not medically relevant.

3.2.6 Active or prior documented autoimmune or inflammatory disorders including but not limited to the following:

- GI Disorders: (including inflammatory bowel disease [e.g. ulcerative colitis, Crohn's disease], diverticulitis (with the exception of a prior episode that has resolved), celiac disease, or other serious gastrointestinal chronic conditions associated with diarrhea.
- Systemic lupus erythematosus
- Wegener's syndrome [granulomatosis with polyangiitis]
- Myasthenia gravis
- Graves' disease
- Rheumatoid arthritis
- Hypophysitis
- Uveitis

The following are exceptions to this criterion: subjects with vitiligo or alopecia; subjects with hypothyroidism (e.g. following Hashimoto syndrome) stable on hormone replacement; or subjects with psoriasis not requiring systemic treatment.

3.2.7 Individuals with a history of a different malignancy are ineligible except for the following circumstances. Note: Individuals with a history of other malignancies are eligible if they have been disease-free for at least 5 years and are deemed by the investigator to be at low risk for recurrence of that malignancy. Individuals with the following cancers are eligible if diagnosed and treated within the past 5 years: non-invasive cancer (such as, any *in situ* cancers) and basal cell or squamous cell carcinoma of the skin.

3.2.8 Female patients who are pregnant (positive  $\beta$ -HCG) or breastfeeding

3.2.9 Prior organ transplant requiring immunosuppressive therapy.

3.2.10 Patients who previously received PD-1 antibody and have experienced toxicities resulting in treatment discontinuation.

3.2.11 Uncontrolled intercurrent illness including, but not limited to, ongoing or active infection, symptomatic congestive heart failure, unstable angina pectoris, cardiac arrhythmia, or psychiatric illness/social situations that would limit compliance with study requirements.

### **3.3 Eligibility Prior to Vaccination with DC/MM fusions and nivolumab**

- 3.3.1 Resolution of all chemotherapy related grade 3-4 toxicity as per CTC criteria 4.0
- 3.3.2 Successful production of at least 2 vaccines of a minimum of  $1 \times 10^6$  fusion cells
- 3.3.3 Absence of disease progression to standard of care therapy during the period of vaccine generation.
- 3.3.4 ECOG performance status  $\leq 2$
- 3.3.5 Participants must have normal organ function as defined below:
  - total bilirubin  $\leq 1.5 \times$  institutional upper limit of normal
  - AST(SGOT)  $\leq 3 \times$  institutional upper limit of normal
  - ALT(SGPT)  $\leq 3 \times$  institutional upper limit of normal
  - creatinine clearance  $\geq 40$  mL/min for participants with creatinine levels above institutional normal.
- 3.3.6 No myeloma therapy within 7 days of initiation of study treatment with the exception of steroids

### **3.4 Inclusion of Women and Minorities**

Both men and women of all races and ethnic groups are eligible for this trial.

## **4. REGISTRATION PROCEDURES**

### **4.1 General Guidelines for DF/HCC Institutions**

Institutions will register eligible participants in the Clinical Trials Management System (CTMS) OnCore. Registrations must occur prior to the initiation of any protocol-specific therapy or intervention. Any participant not registered to the protocol before protocol-specific therapy or intervention begins will be considered ineligible and registration will be denied.

An investigator will confirm eligibility criteria and a member of the study team will complete the protocol-specific eligibility checklist.

Following registration, participants may begin protocol-specific therapy and/or intervention. Issues that would cause treatment delays should be discussed with the Overall Principal Investigator (PI). If the subject does not receive protocol therapy following registration, the subject must be taken off-study in the CTMS (OnCore) with an appropriate date and reason entered.

### **4.2 Registration Process for DF/HCC Institutions**

Applicable DF/HCC policy (REGIST-101) must be followed.

## **5. TREATMENT PLAN**

On this study, patients will be enrolled and undergo tumor collection and dendritic cell collection per protocol. Patients will undergo 1-2 cycles of standard of care therapy during the period of vaccine preparation. Patients for whom vaccine production is successful will undergo vaccination with DC/MM fusions on day 1 of cycle 1, 2, and 3. Subsequent cycles (following cycle 3) will consist of Nivolumab alone on Days 1 and 15 for a total of 6 cycles.

### **5.1 Evaluations Prior to Enrollment**

The following evaluations must be performed within 2 weeks prior enrollment

1. History, physical examination, height and weight
2. ECOG Performance Status
3. Baseline AE Evaluation
4. CBC with differential
5. Liver Functions and blood chemistries: Na, K, Cl, CO2, Ca, Mg, PO4, Creatinine, total bilirubin, direct bilirubin, alkaline phosphatase, AST, ALT, LDH
6. Beta-2 Microglobulin, CRP
7. TSH, Free T4, Free T3
8. Evaluation of creatinine clearance
9. Pregnancy test in FOCBP
10. Laboratory Disease Evaluation:
  - Quantitative serum immunoglobulin levels.
  - Serum protein electrophoresis (SPEP).
  - 24-hour urine collection to determine creatinine clearance and protein excretion, urine electrophoresis (UPEP).
  - Immunofixation of urine and serum protein regardless of SPEP and UPEP results.
  - Serum free light chain ratios (FLC)
11. Bone marrow to assess plasma cell involvement in the marrow as per eligibility criteria. Unilateral bone marrow biopsy and aspirate are required. If performed within 30 days it does not need to be repeated.
12. Skeletal bone survey to include cranium, axial skeleton and proximal long bones or alternative imaging to capture areas of bone disease
13. EKG
14. Vital signs (including ambulatory O2 sat)

## **5.2 Tumor Collection**

Following registration, patients will undergo collection of multiple myeloma cells through bone marrow aspirate collection. Bone marrow aspirates will be obtained (20-30cc) under local anesthesia. If there is an insufficient yield of tumor cells a second collection will be permitted.

At the time of tumor collection, 50ml of plasma in sodium heparin tubes will be collected from the peripheral blood. This will be repeated if a second collection is indicated. Standard infectious serologies will be drawn as per BIDMC practice for storage of cellular products (drawn in 2 red top tubes and 3 pink top tubes and sent to the Stem Cell Lab at BIDMC).

## **5.3 Dendritic Cell Collection**

Patients may receive up to 1 cycle of bridging therapy prior to undergoing leukapheresis. Leukapheresis will be performed when after recovery of blood counts (an ANC >1000 K/uL and PLT >50 K/uL). When possible, leukapheresis will be performed via peripheral access. If peripheral access is inadequate, patients will undergo placement of a temporary central venous catheter. Standard infectious serologies will be drawn within 8 days of isolation dendritic cells as per BIDMC practice for storage of cellular products (drawn in 2 red top tubes and 3 pink top tubes and sent to the Stem Cell Lab at BIDMC).

## **5.4 SOC Anti-Myeloma Bridging Therapy During Period of Vaccine Preparation**

Patients may receive up to 2 cycles of standard of care therapy following leukapheresis. Bridging therapy is at the discretion of the physician, however the use of IMiDs (ie. Lenalidomide or pomalidomide) is prohibited.

## **5.5 Evaluation Prior to Initiation of Immunotherapy**

Patients will be evaluated within 14 days prior to initiation of immunotherapy. The following tests will be performed

at that time:

1. History, physical examination, height and weight
2. ECOG Performance Status
3. AE Assessment
4. Medications
5. CBC with differential, platelet count
6. Liver Functions and blood chemistries: Na, K, Cl, CO2, Ca, Mg, PO4, Creatinine, total bilirubin, direct bilirubin, alkaline phosphatase, AST, ALT, LDH
7. Beta-2 Microglobulin, CRP
8. TSH, Free T4, Free T3
9. Evaluation of creatinine clearance
10. Pregnancy test in females of child bearing potential
11. Laboratory Disease Evaluation:
  - Quantitative serum immunoglobulin levels.
  - Serum protein electrophoresis (SPEP).
  - 24-hour urine collection to determine creatinine clearance and protein excretion, urine electrophoresis (UPEP).
  - Immunofixation of urine and serum protein regardless of SPEP and UPEP results.
  - Serum free light chain ratios (FLC)
12. Bone marrow biopsy and aspirate for re-staging, Note, if marrow was done within prior 6 weeks then this does not need to be repeated.
13. EKG
14. Skeletal bone survey or alternative imaging to include cranium, axial skeleton and proximal long bones or alternative imaging to capture areas of bone disease, if clinically indicated
15. Evaluation of Pre-Treatment Eligibility Criteria and registration to second time point on study.

## **5.6 Day 1 of Cycles 1-3 (+/- 3 days)**

1. History, physical examination, height and weight
2. ECOG Performance Status
3. AE Assessment
4. Medications
5. CBC with differential, platelet count
6. Liver Functions and blood chemistries: Na, K, Cl, CO2, Ca, Mg, PO4, Creatinine, total bilirubin, direct bilirubin, alkaline phosphatase, AST, ALT, LDH
7. Beta-2 Microglobulin, CRP
8. TSH, Free T4, Free T3
9. Evaluation of creatinine clearance
10. Pregnancy test in FOCBP
11. Laboratory Disease Evaluation:
  - Quantitative serum immunoglobulin levels.
  - Serum protein electrophoresis (SPEP).
  - 24-hour urine collection to determine creatinine clearance and protein excretion, urine electrophoresis (UPEP).
  - Immunofixation of urine and serum protein regardless of SPEP and UPEP results.
  - Serum free light chain ratios (FLC)
12. EKG
13. Nivolumab infusion (Per Section 5.12.1)
14. Vaccine administration (Per Section 5.12.2)
15. Vital Signs (including ambulatory O2 sat) per Section 11
16. Study tubes as per Section 10 will be drawn at the pre-immunotherapy visit. They will not be repeated at the start of C1, but will be drawn on day 1 of C2 and C3.

### **5.7 Day 15 of Cycles 1-3 (+/- 3 days)**

1. History, physical examination, height and weight
2. ECOG Performance Status
3. AE Assessment
4. Medications
5. CBC with differential, platelet count
6. Liver Functions and blood chemistries: Na, K, Cl, CO2, Ca, Mg, PO4, Creatinine, total bilirubin, direct bilirubin, alkaline phosphatase, AST, ALT, LDH
7. EKG
8. Nivolumab infusion (Per Section 5.12.1)
9. Vital Signs (including ambulatory O2 sat) per Section 11

### **5.8 Day 1 of Cycle 4 (+/- 3 days)**

1. Bone marrow and aspirate to assess disease response.
2. Bone marrow aspirate for research samples

### **5.9 Day 1 of Cycles 4-6 (+/- 3 days)**

1. History, physical examination, height and weight
2. ECOG Performance Status
3. AE Assessment
4. Medications
5. CBC with differential, platelet count
6. Liver Functions and blood chemistries: Na, K, Cl, CO2, Ca, Mg, PO4, Creatinine, total bilirubin, direct bilirubin, alkaline phosphatase, AST, ALT, LDH
7. Beta-2 Microglobulin, CRP
8. TSH, Free T4, Free T3
9. Evaluation of creatinine clearance
10. Pregnancy test in FOCBP
11. Laboratory Disease Evaluation:
  - Quantitative serum immunoglobulin levels.
  - Serum protein electrophoresis (SPEP).
  - 24-hour urine collection to determine creatinine clearance and protein excretion, urine electrophoresis (UPEP).
  - Immunofixation of urine and serum protein regardless of SPEP and UPEP results.
  - Serum free light chain ratios (FLC)
12. EKG
13. Nivolumab infusion (Per Section 5.12.1)
14. Vital Signs (including ambulatory O2 sat) per Section 11
15. Study tubes as per Section 10

### **5.10 Day 15 of Cycles 4-6 (+/- 3 days)**

1. History, physical examination, height and weight
2. ECOG Performance Status
3. AE Assessment
4. Medications
5. CBC with differential, platelet count

6. Liver Functions and blood chemistries: Na, K, Cl, CO2, Ca, Mg, PO4, Creatinine, total bilirubin, direct bilirubin, alkaline phosphatase, AST, ALT, LDH
7. EKG
8. Nivolumab infusion (Per Section 5.12.1)
9. Vital Signs (including ambulatory O2 sat) per Section 11

## **5.11 Follow Up**

Participants will be followed monthly for the first 6 months following their last dose of treatment. Participants who complete treatment per protocol will be followed as outlined in section 5.11.1 and then followed for Progression Free Survival as outlined in section 5.11.2.

Participants taken off treatment due to toxicity will be followed as outlined in section 5.11.1 and will continue to be followed for Progression Free Survival as outlined in section 5.11.2.

Participants taken off treatment due to disease progression or to start alternative anti-myeloma therapy per MD discretion will be required to do a toxicity assessment visit 30 days after the last dose of study treatment. Participants then will continue to be followed for Survival for 5 years. Requirements for the toxicity assessment visit are outlined in section 5.11.3.

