#### **1.3.2 Secondary Clinical Endpoints**

To determine the clinical response and safety of nivolumab and the DC/MM fusion vaccine in patients with relapsed disease. The percentage of patients achieving complete, very good partial and partial response will be quantified. Minimal residual disease (MRD) status will be determined. Progression free survival (PFS) will be assessed.

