### **5.11.2 Progression Free Survival (+/- 14 days)**

Participants will be followed every 3 months for 5 years. Participants will be followed until time of disease progression, at which time they will be followed for survival as outlined 5.11.4. At the time of disease progression

patients will have disease assessments and study bloods/aspirate as outlined in section 10.

1. Laboratory Disease Evaluation:

- Quantitative serum immunoglobulin levels.
- Serum protein electrophoresis (SPEP).
- 24-hour urine collection to determine creatinine clearance and protein excretion, urine electrophoresis (UPEP) required for participants with +UPEP at baseline. Otherwise, random UPEP is permitted. If the random UPEP is positive, a 24-hour urine collection is required.
- Immunofixation of urine and serum protein regardless of SPEP and UPEP results.

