#### **5.11.3 Toxicity Assessment Visit (+/- 7 days)**

Participants taken off treatment due to disease progression or to start alternative anti-myeloma therapy at MD discretion will be required to do a toxicity assessment visit 30 days after the last dose of study treatment.

1. History, physical examination, height and weight
2. ECOG Performance Status
3. AE Assessment If patients have ongoing related AEs at the toxicity assessment visit, this should continue to be followed at least monthly, or as clinically indicated, until resolution.)
4. Medications
5. CBC with differential, platelet count
6. Liver Functions and blood chemistries: Na, K, Cl, CO2, Ca, Mg, PO4, Creatinine, total bilirubin, direct bilirubin, alkaline phosphatase, AST, ALT, LDH
7. TSH, Free T4, Free T3
8. Evaluation of creatinine clearance
9. Vital Signs (including ambulatory O2 sat) per Section 11

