#### Follow Up

Study Assessments	Toxicity Assessment Visit (+/- 7 days) 	Months 1-6 (+/- 7 days)	Progression Free Survival  (+/- 14 days)	Survival Follow-Up (every 6 months for 5 years)
History, physical exam, weight and height	X	X		
Vital Signs 	X	X		
Ambulatory O2 sat 	X	X		
ECOG performance score	X	X		
CBC, differential, platelet count, and blood chemistries	X	X		
TSH, Free T4, Free T3	X	X		
Evaluation of Creatinine Clearance	X	X		
Quantitative serum immunoglobulins		X	X	
SPEP and immunofixation		X	X	
24 Hour Urine for UPEP, protein excretion and immunofixation		X	X 	
Bone Marrow Biopsy and Aspirate	X	X 	X 	
Serum free light chain ratio		X	X	
B2M, CRP		X		
Toxicity Assessment	X	X		
Skeletal Survey or alternative imaging		X 		
Con Meds	X	X		
Survival status	X			X
Study tubes		X 		

0. Only required for patients who are removed from treatment due to progressive disease or to start alternative anti-myeloma therapy per MD discretion
1. Every 3 months after 6 month follow up visit for 5 years
2. Vitals (BP, HR, Temp, RR, O2 sat) to be taken within 15 minutes prior to start of nivolumab infusion and within 15 minutes following completion.
3. A O2 saturation reading at rest and on exertion should be obtained during each study visit.

4. Only required for participants with +UPEP at baseline, otherwise random UPEP is permitted. If the random UPEP is positive, a 24-hour urine collection is required.
5. At Months 1, 3 and 6 follow up and at time of progression.
6. Months 1 and 6 only
7. Please refer to section 10

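### Patients who switch to other myeloma therapy before progression go to survival-only follow-up in 5.11, contrary to 14.1.3, and section 14 does not say how PFS handles them

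*Combined protocol and SAP*

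**What the plan says.** Section 1.3.2 names the endpoint in one sentence: "Progression free survival (PFS) will be assessed". Section 14 gives no start date, event rule, censoring rule or analysis method for it.

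Section 5.11 sets follow-up by the reason treatment ended:

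- **Completed treatment:** monthly active follow-up (5.11.1), then PFS follow-up (5.11.2).
- **Stopped for toxicity:** the same. "Participants taken off treatment due to toxicity will be followed as outlined in section 5.11.1 and will continue to be followed for Progression Free Survival".
- **Stopped for progression, or to start other therapy:** "Participants taken off treatment due to disease progression or to start alternative anti-myeloma therapy per MD discretion" have the 30-day toxicity visit, and after it "Participants then will continue to be followed for Survival for 5 years".

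PFS follow-up in 5.11.2 is 3-monthly laboratory disease evaluation for up to 5 years, with progression as the exit: "Participants will be followed until time of disease progression, at which time they will be followed for survival as outlined 5.11.4".

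The 30-day visit in 5.11.3 lists no serum or urine electrophoresis, immunofixation, free light chains or marrow. The follow-up calendar in section 11 marks a marrow at that visit but none of the paraprotein or light-chain tests. Its footnote confirms who attends: "Only required for patients who are removed from treatment due to progressive disease or to start alternative anti-myeloma therapy per MD discretion". Survival follow-up (5.11.4) is a clinic or telephone contact every 6 months with no disease assessment.

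Section 14.1.3 describes disease-status follow-up for patients in general, monthly for 6 months and then 3-monthly for 5 years, with no exception for those who switch.

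**The concern.** Patients who switch without progression are grouped with patients whose PFS event has already happened, although theirs has not. From the switch on, nothing scheduled in 5.11 can date their progression. Follow-up for a named endpoint therefore depends on why treatment stopped, and the statistical section is silent on the consequence.

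These are patients with at least 3 prior lines of therapy (3.1.2). It is a reasonable inference, though the plan does not state it, that a physician may change therapy because disease is worsening short of the formal criteria. If the analyst then censors at the switch, the censoring is informative: patients close to progression leave the risk set and are represented by those who stay. Kaplan-Meier PFS would read too long. With one arm and no concurrent control, nothing inside the trial would reveal it.

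**Working it through.** **Step 1. Is there a figure to reproduce?** No. The documents give no PFS median, event count, power or switch rate.

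**Step 2. Follow-up by reason for stopping.**

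| Reason treatment ended | Scheduled paraprotein tests afterwards | Until |
|---|---|---|
| Completed (5.11) | Monthly for 6 months, then 3-monthly | Progression or 5 years |
| Toxicity (5.11) | Same | Same |
| Progression (5.11) | None after the progression work-up | Event already observed |
| Other therapy, no progression (5.11) | None | Event not observed |
| Patients in general (14.1.3) | Disease status monthly, then 3-monthly | 5 years |

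The fourth and fifth rows cannot both apply to a patient who switches.

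**Step 3. Possible effect on PFS.** Every input here is an assumption:

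- PFS is exponential with true median m and is counted from first study treatment.
- A random share f of patients would switch w = 1 month before documented progression.
- m is 3, 4 or 6 months, and f is 10% to 40%.

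Write q = 2^(−w/m), the chance of going one more month without progression. At time t the risk set is proportional to (1−f) + f·q, and observed events come only from the 1−f who do not switch.

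*Censoring at the switch.* The observed hazard is the true hazard × (1−f) / [(1−f) + f·q], so the apparent median is m × [1 + q·f/(1−f)]. For m = 4, q = 2^(−1/4) = 0.841:

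- f = 10%: 4 × (1 + 0.841 × 0.111) = 4.37
- f = 20%: 4 × (1 + 0.841 × 0.250) = 4.84
- f = 30%: 4 × (1 + 0.841 × 0.429) = 5.44
- f = 40%: 4 × (1 + 0.841 × 0.667) = 6.24

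A Kaplan-Meier simulation with 400,000 patients gave 4.38, 4.84, 5.44 and 6.24. For 10% to 40% switchers, the simulated range was 3.3 to 4.6 months for a true median of 3, and 6.6 to 9.6 for a true median of 6.

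*Counting the switch as an event.* The apparent median is m × {1 + log2[1 − f(1−q)]}. For m = 4 and f = 10%, 20%, 30%, 40% this gives 3.91, 3.81, 3.72 and 3.62, as in the simulation.

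*Switching unrelated to progression, f = 20%, m = 4.* Censoring gives 4.0 (no bias). Counting the switch as an event gives 4 × (1 − 0.2) = 3.2; the simulation gave 3.21.

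**Step 4. Limits of the illustration.** As w goes to 0, q goes to 1 and the inflation becomes 1/(1−f), or +11%, +25% and +43% at f = 10%, 20% and 30%. That is the upper case. With w = 1 and m = 4 the corresponding inflation is about +9%, +21% and +36%.

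The 5.11 rule covers only switches that end study treatment, which lasts at most 6 × 28 = 168 days without delays, or about 168/30.4 = 5.5 months. The 4.4 to 5.4 month results fall inside that window. The 6-month results fall beyond it and are therefore too large.

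**The case against.** A reader might infer that the plan censors these patients and that its PFS is therefore biased upwards. The documents do not support that. No section states a PFS censoring rule, and none says whether a switch is an event. Upward bias needs both censoring at the switch and a link between switching and coming progression. The only reason section 5.11 gives is physician discretion, so a switch at the moment progression is suspected is an inference.

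It would also be too strong to say that progression dates in this group are never seen. Laboratory disease evaluation is done on day 1 of every cycle (5.6, 5.9), so progression just before a switch can be documented. The calendar marks a marrow at the toxicity visit, and a rise in marrow plasma cells is one of the progression criteria in 12.2.7. Section 14.1.3, taken literally, would keep these patients under assessment.

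Two objections to the remedy also stand. Progression observed after a switch is progression on the new therapy, so continued testing answers a different question from PFS on the study regimen alone. Counting a switch as an event has a bias of its own, downwards. Neither analysis is simply the correct one.

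What survives is narrower: 5.11 discards scheduled disease data by reason for stopping, it conflicts with 14.1.3, and section 14 leaves the handling open.

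**Conclusion.** The point holds as a gap in follow-up and definition, with a conditional risk of bias. Section 5.11 moves patients who switch without progression to survival-only follow-up, section 14.1.3 says otherwise, and section 14 does not define PFS or the handling of new therapy.

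If these patients are censored at the switch, and if switching foreshadows progression, PFS is overestimated. For an assumed true median of 4 months, a 1-month lead and 10% to 30% switchers, the reading is about 4.4 to 5.4 months. If switching is unrelated to progression, the bias is about zero. The true size cannot be stated from the documents.

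The consequence is small. PFS is a secondary endpoint with no hypothesis or power, in a single-arm study of 25 evaluable patients. The immunologic decision rule, the ORR test and the TLT rule do not use it.

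**What to change.** 1. **Reconcile 5.11 with 14.1.3.** For patients who switch without progression, keep the 5.11.2 laboratory disease evaluation until progression, or at least collect the date of progression. Bring 5.11.3 and the calendar into line on the marrow at the toxicity visit.
2. **Define PFS in section 14:** start date, events, censoring, and the handling of new anti-myeloma therapy. Cover a switch made later, during PFS follow-up, which 5.11.2 does not address.
3. **Report two PFS analyses side by side:** one censoring at the start of new therapy and one counting it as an event. The distance between them shows how far the result depends on handling.
4. **Record the start date of new therapy.** Section 5.14 already requires the date of and reason for leaving treatment, and medications are recorded at the toxicity visit, but the off-treatment date is only a proxy for the start of the next therapy.

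The cost is a few 3-monthly laboratory results in a small number of patients, one extra date field and one extra analysis. The event-counting analysis can understate PFS when switching is unrelated to progression (4.0 read as 3.2 months at 20% in the illustration), so it belongs beside the censored analysis and not in its place.
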